8 SAFETY MONITORING AND ADVERSE-EVENT REPORTING

8.1 Adverse Events

Adverse events (AEs) may occur during the investigational procedure or during the follow-up phase (see **Section 10** for potential risks). Adverse events occurring prior to the use of the NEUROMARK™ System will be documented in the patient's medical record but will not count as related to the investigational device or procedure.

An Adverse Event may occur in users or other persons. Such Adverse Events will be recorded and reported to the Sponsor.

- ☞ Should a user of the device, such as the physician, sustain an injury from the use of the device, the injury would be considered an AE.

Each AE will be judged by the Investigator as to its relationship and level of relatedness to the investigational device and/or investigational procedure. In addition, the Investigator will identify the date of onset, any required treatment or intervention, severity, and duration. All adverse events will be monitored until they are adequately resolved, stabilized and/or explained. Refer to **Table 3** and **Table 4** for Severity and Relationship categories and respective definitions.

The Investigator will use the following (**Table 4**) definitions to rate the severity of each adverse event:

Table 3: Adverse Event (AE) Severity

Severity	Description
Mild	→ awareness of a sign or symptom that does not interfere with the Subject's usual activity or is transient, resolved without treatment and → no sequelae
Moderate	→ interferes with the Subject's usual activity and/or → requires symptomatic treatment
*Severe	→ symptom(s) causing severe discomfort and → significant impact of the Subject's usual activity and → requires treatment

*If event is considered to be a Serious Adverse Event (SAE), the Investigator must report to the Sponsor the SAE within 24 hours of knowledge of the event.

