10.2 Potential Risks

Refer to the manufacturer's labeling for details concerning potential AEs associated with the use of materials, tools or fluid used during the procedure or immediately post-procedure.

Potential risks to the study Subject that may be associated with the use of the NEUROMARK™ System are as follows. Risk of these events is low.

- Allergic or other reaction to device materials or anesthetic (subjects are to be excluded if an allergy/potential allergy is known)
- Trauma to the nasal cavity including

- Mucosal bleeding
 - Mucosal damage
 - Pain/discomfort
 - Synechiae/Adhesions
 - Perforation
- Infection
- Impaired Nasal Function including:
 - Olfactory change
 - Worsening nasal obstruction
 - Septal perforation
 - Worsened eustachian tube function
 - Cosmetic deformity
- Atrophic rhinitis or dry nose
- Headache
- Bone necrosis
- Burn

There may be additional risks related to the local anesthetic including dermal allergic reactions, itching, rash, erythema, stinging and inflammation. Many of these side effects will subside quickly. Systemic side effects are rare and unexpected. They include arrhythmia, hypotension, and a system allergic reaction.

There may be risks related to any post-procedure medication prescribed by the Study Investigator. Those risks can be found on the medication's labeling from the manufacturer.

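### The adverse-event severity table can leave a lasting, non-interfering injury without a grade and caps a severe event that requires no treatment at Moderate

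*Combined protocol and SAP*

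**What the plan says.** Section 8.1 tells the investigator to use the tabulated "definitions to rate the severity of each adverse event". The sentence cites Table 4, but the severity grid is Table 3. Its rows are:

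- **Mild:** "awareness of a sign or symptom that does not interfere with the Subject's usual activity or is transient, resolved without treatment", followed by an underlined *and* and a separate arrow that requires the absence of sequelae.
- **Moderate:** either of two conditions is enough, namely that the event "interferes with the Subject's usual activity" or that it "requires symptomatic treatment"; both may be present.
- **Severe:** all three conditions must hold together: "symptom(s) causing severe discomfort and → significant impact of the Subject's usual activity and → requires treatment".

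The table has no default grade and no rule for an event that meets two rows. The same section has the investigator record any treatment or intervention required, separately from severity.

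Section 10.2 names harms that the device may cause, among them "Septal perforation", "Synechiae/Adhesions" and "Olfactory change". Table 1 schedules nasal endoscopy at 1 and 3 months, so structural findings that the subject has not noticed may be seen.

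Seriousness is a separate judgement, made by outcome in section 8.3. The synopsis bases the safety endpoint on serious events directly attributable to the system at 1 month, and it lists all adverse events, whatever their severity, among the additional evaluations.

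**The concern.** A severity scale that is compulsory for every event should give each event one grade, and a worse event should not receive a lower grade for a reason unrelated to how bad it was. Table 3 fails on both counts.

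First, a lasting local injury that neither limits activity nor needs symptomatic treatment has no clear place. Each site will settle the matter in its own way, and Mild is one likely choice. Second, the need for treatment acts as a gate to the top grade. Section 6.3 leaves post-procedure medication to the investigator's judgement, so what counts as requiring treatment may differ between sites.

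At stake is a field recorded for every adverse event in a study whose primary objective includes safety. Severity also appears in section 16, where an event is unexpected if it was not listed at the severity observed, and section 8.3 makes unexpected events reportable within 24 hours. The definition of an unanticipated adverse device effect and the discontinuation reasons in section 15.1 refer to severity as well.

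**Working it through.** No sample size, power or alpha figure is involved, and the plan gives no figure to reproduce. The check treats the three rows of Table 3 as logical rules and asks which grades each possible event meets.

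**Inputs, all from Table 3.** Five features decide a grade:

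- interference with usual activity: none, some or significant (3 levels);
- severe discomfort: yes or no (2);
- treatment required: yes or no (2);
- transient or not, and sequelae or not: three combinations, because transient with sequelae is excluded as contradictory.

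This gives 3 × 2 × 2 × 3 = 36 profiles. They are logical types, not frequencies.

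**Rules.** Moderate is met if there is any interference or treatment is required. Counting any required treatment as symptomatic favours the plan. Severe is met if severe discomfort, significant interference and required treatment are all present. Mild can be read in three ways:

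- A: (no interference or transient), and no treatment, and no sequelae.
- B: (no interference, or transient without treatment), and no sequelae.
- C: no interference, or (transient, without treatment, without sequelae).

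A and B respect the separate arrow for sequelae. C attaches that condition to transient events only.

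| Grades met | A | B | C |
|---|---|---|---|
| None | 2 | 2 | 0 |
| Mild only | 4 | 4 | 6 |
| Moderate only | 23 | 19 | 17 |
| Mild and Moderate | 4 | 8 | 10 |
| Moderate and Severe | 3 | 3 | 3 |
| Total | 36 | 36 | 36 |

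**Gap 1.** Under A and B the two ungraded profiles have sequelae, no interference and no treatment required; one is without severe discomfort and one is with it. The first is the small perforation, adhesion or smell change that does not trouble daily activity. Sequelae rule out Mild, nothing satisfies Moderate, and Severe is far off. Under C the gap closes, but only because the permanent injury becomes Mild.

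**Gap 2.** Three profiles combine severe discomfort with significant interference and no treatment required. All three fail Severe and meet Moderate under every reading. The transient one also meets Mild.

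**Overlap.** Profiles meeting more than one grade number 4 + 3 = 7 under A, 8 + 3 = 11 under B and 10 + 3 = 13 under C. The three that meet both Moderate and Severe would be settled by a highest-grade rule, but the plan states none.

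**The case against.** The strongest reply is that nothing decisive depends on this grade, and much of that stands. The safety endpoint counts serious events, classified in section 8.3 by outcomes that include permanent damage. A lasting but non-serious finding is still an adverse event. It is recorded with its onset, duration and any treatment required, and followed until resolved, stable or explained. No harm goes uncollected.

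It can also be said that a perforation is the event itself and not a sequela of it. The protocol does not define sequelae, so the point is arguable. But on that view a permanent injury is Mild, the same result as reading C, so the row still needs rewording.

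Four stronger readings are tempting, and the documents do not support them:

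- A reader might infer that an event is Severe only if treatment was given. The criterion is need, not receipt. An event that needed treatment which the subject declined could still be Severe.
- A reader might infer that the harms listed in section 10.2 generally go ungraded. Any that interferes with activity or needs symptomatic treatment is at least Moderate. Only lasting findings with neither can fall through.
- A reader might infer that a reported rate of severe events will be too low. Section 11 plans no tabulation by severity and no severe-event rate, so no bias in percentage points can be stated.
- A reader might infer that the primary safety result is affected. It is not, because seriousness and severity are separate judgements.

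**Conclusion.** The point holds as a defect in a stated rule with secondary impact. On the readings that fit the table's layout, 2 of 36 profiles receive no grade; on the third reading they are graded Mild despite lasting injury. On every reading, a severely uncomfortable, activity-limiting event that requires no treatment is Moderate at most. Between 7 and 13 of 36 profiles meet more than one grade, with no rule to choose.

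The conclusion rests on two assumptions: that a lasting injury counts as a sequela (if it does not, it is Mild), and that symptomatic treatment in the Moderate row covers any treatment. Read literally, the second would widen the gap, since a symptomless injury that needs repair would also fit no row.

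How often such events occur cannot be judged from the documents. The effect is limited to the severity field and the definitions that mention severity. Even there the link is loose, because section 10.2 lists its harms without grades.

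**What to change.** Reword Table 3 so that every event receives exactly one grade:

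- **Severe:** severe discomfort together with significant impact on usual activity, whether or not treatment is required. The need for treatment is already captured elsewhere under section 8.1.
- **Moderate:** any interference with usual activity, or any treatment required, symptomatic or not, or a sequela or lasting finding, where Severe is not met.
- **Mild:** none of these.
- Add one line: assign the highest grade whose criteria are met.
- Record sequelae (yes or no) as a separate adverse-event field.
- In the same edit, correct the section 8.1 reference from Table 4 to Table 3.

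Applied to the same 36 profiles, Mild covers those with no interference, no treatment and no sequelae: 2 (transient or not) × 2 (severe discomfort or not) = 4. Severe covers 2 (treatment required or not) × 3 (transient and sequelae combinations) = 6. Moderate takes the remaining 36 − 4 − 6 = 26. None is ungraded and none has two grades. Severe discomfort with no interference, treatment or sequelae stays Mild, as now; if the sponsor does not intend that, it should say so in the table.

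The cost is table wording, one case report form field and a line in site training. The downside is that slightly more events may be graded Moderate or Severe.

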8.2 Assessment of Relationship

The Investigator will use the following definitions to assess the relationship of the AE to the use of the NEUROMARK™ System.

The Investigator will determine if the adverse event is related to the study procedure, the investigational device and/or a pre-existing condition as described below (**Table 5**).

Table 4: Adverse Event Relationship

AE Related to:	Description
Study Procedure	An AE that is the result of / or related to the study procedure but not necessarily the NEUROMARK™ System..
Investigational Device	An AE that is a result of / or related to use of the NEUROMARK™ System.
Pre-existing Condition	An AE that is a result of / or related to a pre-existing condition or injury.

The Investigator will then determine the adverse event relationship to the study device and the relationship to the study procedure as described below (**Table 5**) and (**Table 7**).

Table 5: Adverse Event (AE) Device Relationship

Relationship	Description
Not Related	
 → not associated with study device → due to an underlying or concurrent illness or effect of another device or drug
Unlikely	
 → little or no temporal relationship to the study device and/or → a more likely alternative etiology exists
Possible	
 → temporal sequence between device application and event → is such that the relationship is not unlikely or → Subject's condition or concomitant therapy could have caused the AE
Probable	
 → temporal sequence is relevant or → event abates upon device application completion/removal or → event cannot be reasonably explained by the Subject's condition
Highly Probable	
 → temporal sequence is relevant and → event abates upon device application completion/removal or reappearance of the event on repeat device application
Related	
 → temporal sequence is relevant and → the adverse event is directly related to the use of the NEUROMARK™ System

Table 6: Adverse Event (AE) Procedure Relationship

Relationship	Description
Not Related	
 → not associated with study procedure → due to an underlying or concurrent illness or effect of another device or drug
Unlikely	
 → little or no temporal relationship to the study procedure and/or → a more likely alternative etiology exists
Possible	
 → temporal sequence between procedure and event → is such that the relationship is not unlikely or → Subject's condition or concomitant therapy could have caused the AE
Probable	
 → temporal sequence is relevant or → event abates upon procedure completion or → event cannot be reasonably explained by the Subject's condition
Highly Probable	
 → temporal sequence is relevant and → event abates upon procedure completion/removal or reappearance of the event on repeat device application

Relationship	Description
Related	→ temporal sequence is relevant and → An adverse event that is not directly related to the use of the NEUROMARK™ System but is directly attributable to the procedure in which Neuromark was used.

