Study Endpoints:	
Safety will be evaluated based on frequency of Serious Adverse Events (SAEs) directly attributable to the NEUROMARK™ System at one (1) month post index procedure.
 
Efficacy will be assessed by the change in Visual Analog Scale (VAS) Nasal Symptom Score (NSS) from baseline through 3 months for rhinorrhea and nasal congestion.

Additional Evaluations:	
Additional information, as listed below, will be collected and the resulting data analyzed and reported for each follow-up, as applicable.
 
• A change in the VAS NSS from baseline.• A change in reflective Total Nasal Symptom Score (rTNSS) from baseline for rhinorrhea.• A change in rTNSS from baseline for nasal congestion.• A change in rTNSS from baseline.• A change in Postnasal Drip (PND) from baseline.• A change in Quality of Life (mini-Rhinoconjunctivitis Quality of Life Questionnaire (RQLQ) from baseline.• Procedure tolerability (e.g., discomfort, length of procedure)• Individual symptoms (e.g., post-nasal drip, nasal itching, sneezing)• Responder rates.• Patient satisfaction (e.g., patient reported symptom relief)• Endoscopic assessment.• Post-procedure discomfort (e.g., headache, facial pain, ear pain/blockage).• All adverse events regardless of severity or relatedness. 
All subjects who undergo treatment will be followed to 1 year for informational purposes and any study related findings will be reported.

Anticipated Duration:	
The study is anticipated to begin enrollment in Q1 of 2022 with enrollment complete in Q2 of 2022. The last patient visit is expected to take place by or during Q2 of 2023.

Study Evaluations:	Table 1 provides an overview of all protocol-related activities the Subject can expect to undergo as part of study participation.
Indications for Use	The NEUROMARK™ System is indicated for use in otorhinolaryngology (ENT) surgery for creation of radiofrequency (RF) lesions to disrupt posterior nasal nerves in patients with chronic rhinitis.
Intended Use:	The NEUROMARK™ System is intended for the application of Radiofrequency energy to create lesions in mucosal tissue in otolaryngological [also known as Ear, Nose and Throat (ENT)] procedures in patients with chronic rhinitis.

Screening Considerations:

- If data are available at baseline and the information collected per protocol, the existing data may be used to support patient screening. The test/assessment may not need to be redone.

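### Table 6 defines a procedure-related event as one not directly related to the device, against Sections 8.1 and 8.2 and Table 4, so procedure attribution is understated for dual-cause events and a serious one could be misclassified out of the safety endpoint

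*Combined protocol and SAP*

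**What the plan says.** Three places let an event have both causes. Section 8.1 has the investigator judge each event's "relationship and level of relatedness to the investigational device and/or investigational procedure". Section 8.2 has the investigator decide whether it is "related to the study procedure, the investigational device and/or a pre-existing condition". Table 4 describes the procedure category as "An AE that is the result of / or related to the study procedure but not necessarily the NEUROMARK™ System".

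Section 8.2 then requires two gradings: "The Investigator will then determine the adverse event relationship to the study device and the relationship to the study procedure". The device scale is Table 5. The text points to Table 7 for the procedure scale, but that scale is Table 6. Each scale has six grades, from *Not Related* to *Related*.

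For *Related*, both tables require relevant timing plus a second condition:

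- Table 5 (device): "the adverse event is directly related to the use of the NEUROMARK™ System".
- Table 6 (procedure): "An adverse event that is not directly related to the use of the NEUROMARK™ System but is directly attributable to the procedure", with the procedure identified as the one in which the device was used.

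The safety endpoint in the Protocol Synopsis is the "frequency of Serious Adverse Events (SAEs) directly attributable to the NEUROMARK™ System at one (1) month post index procedure". The same synopsis lists all adverse events, of any severity or relatedness, among the additional evaluations.

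**The concern.** The top grade of the procedure scale contains a statement about the device. Nothing in Sections 8.1 and 8.2 or Table 4 prepares the investigator for this, since all of them treat device and procedure as causes that may coexist. Coexistence is also likely in practice: under Section 6.1 the procedure starts once the subject is anesthetized and is complete when the system is removed, so most of it is device use.

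Two things are at stake. The first is the accuracy of the procedure grade for an event with both causes. The second is the safety endpoint, which depends on attribution to the device. If a grade on the procedure scale carries a denial of direct device causation, an entry on one scale can affect a count that should rest on the other. Relatedness is judged by the investigator, and the protocol text describes no independent adjudication of it.

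**Working it through.** The plan states no figure on this point, so the check is a comparison of definitions, followed by an illustration of size.

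**Step 1: the definitions side by side.** Take an event directly caused by both device and procedure.

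| Place | Are both causes allowed? |
|---|---|
| Section 8.1 | Yes (and/or) |
| Section 8.2, lead-in to Table 4 | Yes (and/or) |
| Table 4, Study Procedure | Yes (not necessarily the device) |
| Table 5, *Related* | Yes (requires a direct device relation, silent on the procedure) |
| Table 6, *Related* | No (requires no direct device relation) |

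**Step 2: which grade pairs are lost.** Six device grades by six procedure grades give 6 × 6 = 36 pairs (the match with the 36 subjects is a coincidence). Table 6 rules out exactly one, *Related*/*Related*, which is the pair that describes an event directly caused by both.

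**Step 3: the procedure grade that remains.** With device *Related*, the next procedure grade down is *Highly Probable*. It needs the event to abate on completion or removal, or to reappear on repeat device application. A lasting injury such as a perforation or burn (both listed in Section 10.2) need not abate at completion, and Section 6.1 provides for a single treatment session. Such an injury can reach only *Probable*, which needs just one of three alternatives, relevant timing among them. Table 6 is also at odds with itself: *Highly Probable* accepts recurrence on device re-application as evidence for a procedure relation, while the grade above it excludes a direct device relation.

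**Step 4: the effect on the endpoint.** There are two ways to grade a serious dual-cause event.

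- (a) Device *Related*, procedure *Highly Probable* or lower. The event stays in the endpoint and only the procedure attribution is understated.
- (b) Procedure *Related*. By its wording this records that the event was not directly related to the device, which places it outside the endpoint definition.

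**Step 5: the size of (b).** Inputs: 36 treated subjects (Section 11.2), all in the safety analysis (Section 11). The number x of subjects with a serious dual-cause event is not in the documents; 0 to 2 is assumed, with no other qualifying events. The exact (Clopper-Pearson) 95% limits are the 2.5% quantile of Beta(x, 36 − x + 1) and the 97.5% quantile of Beta(x + 1, 36 − x), with a lower limit of 0 when x = 0.

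| x | Counted | If graded as in (b) |
|---|---|---|
| 0 | 0/36 = 0% (0 to 9.7%) | no change |
| 1 | 1/36 = 2.8% (0.1 to 14.5%) | 0/36 = 0% (0 to 9.7%) |
| 2 | 2/36 = 5.6% (0.7 to 18.7%) | 0/36 = 0% (0 to 9.7%) |

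Each reclassified event moves the result by 1/36 = 2.8 percentage points.

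**The case against.** The strongest reply is that the endpoint is safe if the tables are followed. Table 5 *Related* contains no procedure exclusion, so a dual-cause event qualifies for it. Table 6 *Related* is then unavailable by its own terms, and route (b) is a misapplication. This stands. A reader might infer that the tables force a serious dual-cause event out of the endpoint, and the documents do not support that.

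A reader might also infer that such an event has no usable procedure grade. That is too strong as well. One pair of 36 is barred, and device *Related* with procedure *Probable* records both causes. What is lost is the strength of the procedure attribution.

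It can further be said that Table 6 *Related* works as a residual grade for harms of the procedure apart from the device. Section 10.2 does list anesthetic risks separately, and lists bleeding, perforation and burn as risks of using the System, which points the investigator to Table 5. That reading is coherent, but the protocol does not state it. It also leaves the conflict with the and/or wording and Table 4, which call for a scale of procedure causation in its own right.

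Finally, no event disappears: all adverse events are reported whatever their relatedness, and serious ones go to the sponsor within 24 hours. The plan sets no safety threshold or performance goal, so no decision rule turns on 0/36 against 1/36. Both points are right and limit the consequence. The all-event listing does not, however, correct the endpoint count or the recorded attribution.

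**Conclusion.** The definition is wrong as written. Table 6 *Related* contradicts Sections 8.1 and 8.2 and Table 4, and following it understates the procedure attribution of any event directly caused by both device and procedure. This rests on the text alone.

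The effect on the safety endpoint is a misclassification risk and no more. It arises only if an investigator picks procedure *Related* for an event that was also directly device-related. The risk is heightened because, among the relationship tables, only Table 6 *Related* uses the endpoint's phrase for direct attribution, and there it refers to the procedure. Under the assumption of one such serious event among 36 subjects, the reported rate would fall from 2.8% to 0%, and the upper 95% limit from 14.5% to 9.7%. The true number of such events may be zero.

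**What to change.** Keep the timing condition in Table 6 *Related* and replace the second condition: the event is directly attributable to the study procedure, whether or not it is also related to the NEUROMARK System. Below the tables, state that Tables 5 and 6 are graded independently, that a procedure grade never lowers the device grade, and that the safety endpoint is counted from the Table 5 device grade alone. The protocol does not say which Table 5 grades count as direct attribution. The rewording does not settle this, so the sponsor should name those grades in the same edit.

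The cost is one table row and a short statement in the protocol, carried into the CRF completion guidelines. The downside is that some events will appear under both device and procedure, so the two counts must not be added together. That overlap is what the and/or wording already implies.
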